### **Objective Response (OR)**

Objective response is defined as a complete response (CR) or partial response (PR) according to (RECIST v.1.1; Appendix 2) recorded from randomization until disease progression assessed by BICR or death due to any cause. Both CR and PR must be confirmed by repeat assessments performed no less than 4 weeks after the criteria for response are first met. A patient will be considered to have achieved an OR if the patient has a sustained complete response (CR) or partial response (PR) according to RECIST v.1.1 definitions. Otherwise, the patient will be considered as a non-responder in the OR rate analysis. Additionally, patients with inadequate data for tumor assessment (eg, no baseline assessment or no follow-up assessments) will be considered as non-responders in the OR rate analysis.

The OR rate (ORR) on each randomized treatment arm will be estimated by dividing the number of patients with objective response (CR or PR) by the number of patients randomized to the respective treatment arm. The corresponding exact 2-sided 95% CIs will be provided by treatment arm.

In addition, the best overall response for each patient will be summarized by treatment arm.

### **Disease Control (DC)**

Disease control (DC) is defined as complete response (CR), partial response (PR), or stable disease (SD) according to the RECIST v.1.1 (Appendix 2) recorded from randomization until disease progression assessed by BICR or death due to any cause. DC at 24 weeks is defined as CR, PR or SD  $\geq 24$  weeks after randomization and prior to disease progression assessed by BICR or death due to any cause.

The DC rate (DCR) and DCR at 24 weeks on each randomized treatment arm will be estimated by dividing the number of patients with CR, PR, or SD overall or  $\geq 24$  weeks by the number of patients randomized to the treatment arm. The corresponding exact 2-sided 95% CIs for DCR and DCR at 24 weeks will be provided by treatment arm.

### **Time to Tumor Response (TTR)**

Time to tumor response (TTR) is defined, for patients with an objective response per RECIST v1.1 (Appendix 2), as the time from randomization to first documentation of objective tumor response (CR or PR).

TTR will be summarized by treatment arm using descriptive statistics (n, mean, median, standard deviation, minimum, and maximum).

### **Duration of Response (DR)**

Duration of response (DR) is defined, for patients with an objective response per RECIST v. 1.1 (Appendix 2), as the time from the first documentation of objective tumor response (CR or PR) to the first documentation of objective tumor progression assessed by

BICR or death due to any cause, whichever occurs first. Censoring rules for DR will follow those described above for PFS.

DR will be summarized by treatment arm using Kaplan-Meier method and displayed graphically, where appropriate. The median DR and 95% CI for the median will be provided for each treatment arm.

### **PFS on next-line therapy (PFS2)**

PFS2 is defined as the time from randomization to discontinuation of next-line treatment, second objective disease progression, or death from any cause, whichever occurs first. PFS2 will be summarized by treatment arm using Kaplan-Meier methodology and displayed graphically, where appropriate. The median PFS2 and 95% CI for the median will be provided for each treatment arm.

### **Patient-Reported Outcomes (PRO)**

The FKSI and EuroQol 5-Dimension (EQ-5D) will be scored according to their respective validation papers and user's guides.

For the FKSI-19, in addition to assessing median change over time between the two treatment groups, a time to deterioration analysis is planned, for the FKSI-DRS. A 3 point change (within group) and a 2 point difference (between groups) has been established as clinically meaningful for this 9-item subscale. Time to 3 point deterioration of FKSI-DRS will be analyzed by a log-rank test stratified by randomization stratification factors. The time to deterioration associated with each treatment arm will be summarized using the Kaplan-Meier method and displayed graphically where appropriate. Confidence intervals (CIs) for the 25th, 50th and 75th percentiles will be reported. The Cox proportional hazards model will be fitted to compute the treatment hazard ratios and the corresponding 95% CI. The EuroQoL EQ-5D consists of 2 parts, the EQ-5D index (or simply EQ-5D) and EQ-VAS. The EQ-5D comprises 5 dimensions of health (mobility, self-care, usual activities, pain or discomfort, and anxiety or depression). A unique EQ-5D health state is defined by combining one level from each of the 5 dimensions and is converted to a single summary index or health utility value. The EQ-VAS is a visual analog scale where the patient indicates how good or bad his health is today by marking an appropriate point on a line between 0 to 100, which correspond to the worst and best imaginable health states.

Missing values in the PRO instruments FKSI and EQ-5D will be handled following the guidance from their respective User Manuals. For the FKSI multi-item scales, the score may be imputed as the mean of the non-missing questions if at least half the questions in that scale are answered. For EQ-5D, the entire score for that cycle is deemed missing if the answer to any one of the 5 dimensions is missing. EQ-5D will be analyzed by using repeated measures model.

### **Pharmacokinetic Analysis of Avelumab and Axitinib (Arm A Only)**

Standard plasma PK parameters for axitinib will be estimated using non-compartmental analysis. For axitinib, standard PK parameters will include  $C_{max}$  and  $C_{trough}$ . Descriptive statistics for the PK parameters for axitinib will be provided by dose, cycle and day of assessment in tabular form.

Axitinib  $C_{trough}$  and  $C_{max}$  plasma concentrations will be summarized descriptively (n, mean, SD, CV, median, minimum, maximum, geometric mean, its associated CV, and 95% confidence interval) by dose, cycle, and day. The trough concentrations for axitinib will be plotted for each dose using a box-whisker plot by cycle and day in order to assess the attainment of steady state.

Avelumab  $C_{trough}$  plasma concentrations will be summarized descriptively (n, mean, SD, CV, median, minimum, maximum, geometric mean, its associated CV, and 95% confidence interval) by dose, cycle, and day. The trough concentrations for avelumab will be plotted for each dose using a box-whisker plot by cycle and day in order to assess the attainment of steady state.

The central laboratory, analytical laboratory, and Pfizer clinical assay group colleagues will be unblinded; avelumab and axitinib PK samples collected from Arm A (investigational arm) will be sent to the analytical lab for analysis. If the need arises for an early analysis of the PK data (before database lock and release of the randomization codes for the study), a PK unblinding plan will be developed. A PK analyst, who is not associated with the study team, will conduct the analysis to avoid unblinding of the study team.

### **Immunogenicity Assessment (Arm A Only)**

For the immunogenicity data, the percentage of patients with positive ADA and neutralizing antibodies each will be reported. For patients with positive ADA, the magnitude (titer), time of onset, and duration of ADA response will also be described, if data permit.

Because the observed incidence of ADA is highly dependent on multiple factors including the assays used for ADA detection, timing of sample collection and immune status of the patients, the incidence of ADA observed in the planned study may differ from the incidence reported in historical clinical trials.

### **Population Pharmacokinetic and Exposure Response Analysis**

Avelumab disposition will be evaluated using a population PK model for the drug and the relationship between exposure and efficacy and safety endpoints will be explored, as necessary, based on emerging efficacy and safety data. The results of these modeling analyses may be reported separately from the clinical study report.

## **Analysis of Biomarker Endpoints**

Biomarker status (ie, positive or negative) may be determined by a predictive biomarker test with an established scoring algorithm defining positive and negative that is developed by the Sponsor. Analysis of primary and secondary efficacy endpoints in sub-groups defined by biomarker status will be performed and reported as described above. Comparisons will be made between biomarker sub-groups (positive and negative) within treatment arms and between treatment arms within biomarker sub-groups.

### **9.4. Analysis of Other Endpoints**

Descriptive statistics will be used to summarize all patient characteristics, treatment administration/compliance, safety parameters, and biomarkers. Data will also be displayed graphically, where appropriate.

#### **9.4.1. Statistical Analysis of Biomarker Endpoints**

Biomarkers will be assessed separately for whole blood, serum, plasma, archival tumor tissue, and de novo tumor biopsies. In each case, summaries of baseline levels, changes from baseline (where appropriate), gene alteration or biomarker signature status, will be reported. For continuous variables summary statistics may include the mean, ratio to baseline, standard deviation, median, 25th and 75th quartile, %CV and minimum/maximum levels of biomarker measures; for categorical variables, summary may include number and percentage, odds ratio as appropriate.

Data from biomarker assays will be analyzed using graphical methods and descriptive statistics such as linear regression, t-test, and analysis of variance (ANOVA). The statistical approach may examine correlations of biomarker results with pharmacokinetic parameters and measures of anti-tumor efficacy.

[REDACTED]

[REDACTED]

[REDACTED]

### **9.5. Safety Analysis**

The Safety Analysis Set will be the primary population for safety evaluation. Summaries of AEs and other safety parameters will be provided, by treatment arm, as appropriate.

## **Adverse Events**

Adverse events will be classified using the medical dictionary for regulatory activities (MedDRA) classification system. The severity of the toxicities will be graded according to the NCI CTCAE v4.03 whenever possible (<http://ctep.info.nih.gov/reporting/ctc.html>). The frequency of patients experiencing treatment emergent adverse events corresponding to body systems and MedDRA preferred term will be reported. Adverse events will be graded by worst NCI CTCAE v4.03 Grade. Adverse events will be summarized by cycle and by relatedness to study treatment.

Emphasis in the analysis will be placed on AEs classified as treatment emergent. Adverse events leading to death or discontinuation of study treatment, events classified as NCI CTCAE v4.03 Grade 3 or higher, trial drug-related events, and serious adverse events will be considered with special attention. As appropriate, the difference in risk between treatment arms for AEs of clinical interest may be further assessed as described in the SAP.

Detailed information collected for each AE will include a description of the event, duration, whether the AE was serious, intensity, relationship to study treatment, action taken, and clinical outcome.

### **Time to treatment discontinuation/failure due to toxicity**

Time to treatment discontinuation/failure due to toxicity is defined as the time from first dose of study treatment to discontinuation of study treatment due to an adverse event or death due to study treatment toxicity. Time to treatment discontinuation/failure due to toxicity will be summarized by treatment arm using Kaplan-Meier methodology and displayed graphically, where appropriate. The median time to treatment discontinuation/failure due to toxicity and 95% CI for the median will be provided for each treatment arm.

### **Treatment discontinuation due to toxicity**

Treatment discontinuation due to toxicity is defined as the discontinuation of study treatment due to an adverse event or death due to study treatment toxicity. The rate of treatment discontinuation due to toxicity in each treatment arm will be estimated by dividing the number of patients who meet the above criteria by the number of patients in the safety set. The corresponding exact 2-sided 95% CIs will be provided for each treatment arm.

### **Laboratory Abnormalities**

The laboratory results will be graded according to the NCI CTCAE v4.03 severity grade. The frequency of patients with laboratory test abnormalities will be summarized according to the worst grade for each laboratory test.

For laboratory tests without an NCI CTCAE grade definition, results will be categorized as normal (within normal ranges), abnormal, or not done.

Shift tables will be provided to examine the distribution of laboratory abnormalities.

## **MUGA or ECHO**

Reports and assessments of cardiac function will be recorded. MUGA or ECHO scan results will be summarized using NCI CTCAE version 4.03 by treatment group.

### **Electrocardiograms**

ECG measurements (an average of the triplicate measurements) will be used for the statistical analysis and all data presentations. Any data obtained from ECGs repeated for safety reasons after the nominal time-points will not be averaged along with the preceding triplicates. Interval measurements from repeated ECGs will be included in the outlier analysis (categorical analysis) as individual values obtained at unscheduled time points.

QT intervals will be corrected for heart rate (QTc) using standard correction factors [ie, Fridericia's (default correction), Bazett's, and possibly a study specific factor, as appropriate]. Data will be summarized and listed for QT, HR, RR, PR, QRS, QTc.

Descriptive statistics (n, mean, median, standard deviation, minimum, and maximum) will be used to summarize the absolute corrected QT interval and changes from baseline in corrected QT after treatment. Categorical analysis will be conducted for the maximum change from baseline in corrected QT and the maximum post-baseline corrected QT interval.

Shift tables will be provided for baseline vs worst on treatment corrected QT. Shift tables will also be provided for ECG abnormality at baseline vs. on treatment. Patients experiencing clinically-relevant morphological ECG changes will be summarized (including frequency and percentage).

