13.	Serum/Urine Pregnancy Test: For female patients of childbearing potential, a serum pregnancy test, with sensitivity of at least 25 mIU/mL, will be performed on two occasions prior to starting study treatment: once at the start of screening and once at the baseline visit immediately before investigational product administration. During treatment, pregnancy tests (serum or urine test) will also be routinely repeated on Days 1, 15, and 29 of each treatment cycle during the active treatment period and additionally whenever one menstrual cycle is missed or when potential pregnancy is otherwise suspected. Additional pregnancy tests may also be undertaken if requested by IRB/ECs or if required by local regulations. Results of the pregnancy test should be evaluable prior to each dosing. (see Section 7.1.1 ).
14.	Urinalysis (Table 7): Required only at Screening. If protein $\geq 2+$ by semiquantitative method (eg, urine dipstick), protein will have to be quantified by 24 hour urine collection. To be performed as clinically indicated at other timepoints.

15. **12-Lead ECG:** See [Section 7.1.5](#) for details. All patients require a triplicate ECG measurement at screening. On-treatment ECGs will be performed on Days 1, 15, and 29 of Cycle 1 before avelumab infusion and at the end of infusion in Arm A and before sunitinib drug intake in Arm B. At each time point, 3 consecutive 12-lead ECGs (triplicates) will be performed approximately 2 minutes apart to determine mean QTc (average of triplicates). If patient experiences a cardiac or neurologic AE (specifically syncope, dizziness, seizures, or stroke), triplicate ECGs should be obtained at time of the event. If the mean QTc is prolonged ( $>500$  msec), the ECGs should be re-evaluated by a qualified person at the institution for confirmation and repeated as clinically indicated. Additional triplicate ECGs may be performed as clinically indicated. At that time, creatinine kinase (CK) and troponin should be performed in association with clinically indicated ECG assessments. When coinciding with blood sample draws for pharmacokinetics (PK), ECG assessment (as well as CK and troponin, if clinically indicated) should be performed prior to PK blood sample collection, such that the PK blood sample is collected at the nominal time.

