9. **Thyroid Function Tests:** Free T4 and TSH tests will be performed at End of Treatment/Withdrawal visit and Follow-up visits at 30 ±3, 60 ±3, and 90 ±3 days after the last dose. Additional tests should be performed when clinically indicated. See Table 7.
10. **ACTH Test:** ACTH tests will be performed at End of Treatment/Withdrawal visit and Follow-up visit at 30 ±3, 60 ±3, 90 ±3 days after the last dose. Additional tests should be performed when clinically indicated. See Table 7.
11. **Serum/Urine Pregnancy Test:** For female patients of childbearing potential, a serum or urine pregnancy test, with sensitivity of at least 25 mIU/mL, will be performed at the End of Treatment/Withdrawal visit and at 30 ±3, 60 ±3 (Arm B only). Days Follow-up visit and additionally whenever one menstrual cycle is missed or when potential pregnancy is otherwise suspected. Additional pregnancy tests may also be undertaken if requested by IRB/ECs or if required by local regulations.
12. **Urinalysis:** Required only at the End of Treatment. To be performed as clinically indicated at other timepoints.
13. **12-Lead ECG:** See [Section 7.1.5](#) for details. Triplicate ECG measurements should be performed at end of treatment, and when clinically indicated. Creatinine kinase (CK) and troponin should be performed in association with clinically indicated ECG assessments. Clinically significant findings seen on follow-up ECGs should be recorded as adverse events.

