The last available assessment prior to the start of study treatment is defined as 'baseline' value or 'baseline' assessment for safety analyses. If an assessment is planned to be performed prior to the first dose of study treatment in the protocol and the assessment is performed on the same day as the first dose of study treatment, it will be assumed that it was performed prior to study treatment administration, if assessment time point is not collected or is missing. If assessment time points are collected, the observed time point will be used to determine pre-dose on study day 1 for baseline calculation. Unscheduled assessments will be used in the determination of baseline. However, if time is missing, an unscheduled assessment on study day 1 will be considered to have been obtained after study treatment administration.

Patients who start treatment and discontinue from the study on the same day may have two different sets of data collected on study day 1 (one during study and one in the End of Treatment (EOT) visit). Data reported at the EOT visit are not eligible for baseline selection.

If a scheduled pre-dose measurement actually occurred post-dose, then the corresponding measurement will be treated and analyzed similar to an unscheduled post-dose measurement.

Baseline for RR and QT/QTc interval assessments will be derived from the visit where both RR and QT are not missing. Triplicate ECGs are collected in the study and the baseline for each ECG measurement is the average of the pre-dose replicate measurements on the baseline day. Unscheduled assessments will not be included in the calculation of the average. QTcB and QTcF will be derived based on RR and QT. The average of the replicate measurements will be determined after the derivation of the individual parameter at each time point.

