6.6.10. Electrocardiogram

ECG summaries will include all ECG assessments from the on-treatment period. All ECG assessments will be listed, and those collected outside the on-treatment period will be flagged in the listing. QTcB and QTcF will be derived based on RR and QT (see below). The average of the replicate measurements should be determined after the derivation of the individual parameter at each time point.

Selecting Primary QT Correction for Heart Rate

The analysis of QT data is complicated by the fact that the QT interval is highly correlated with heart rate. Because of this correlation, formulas are routinely used to obtain a corrected value, denoted QTc, which is independent of heart rate. This QTc interval is intended to represent the QT interval at a standardized heart rate. Several correction formulas have been proposed in the literature. For this analysis we will use some of those methods of correction, as described below. The QT interval corrected for heart rate by the Bazett's formula, QTcB, is defined as

$$QTcB = \frac{QT}{\sqrt{RR}},$$

the QT interval corrected for heart rate by the Fridericia's formula, QTcF, is defined as

$$QTcF = \frac{QT}{\sqrt[3]{RR}},$$

where RR represents the RR interval of the ECG, in seconds, and can be estimated as 60/Heart Rate.

Although Bazett's correction is the historical standard, it does not perform well when heart rate fluctuates. Fridericia's formula may perform better under these conditions. If QTcB and QTcF methods do not adequately correct for HR and there are a sufficient number of patients (e.g. >30) with baseline ECGs, an alternate correction to achieve the goal of getting uncorrelated QTc and RR is based on a linear regression methods which yields, theoretically, uncorrelated QTc and RR.

Linear regression method:

- Fit a model $QT = a + b \times RR$ to baseline data
- Use the estimated slope, \hat{b} , to correct QT
- Corrected QT for heart rate will be computed as follows:

$$QTcP = QT + \hat{b} \times (1 - RR)$$

Data will be summarized using QTcF and QTcB. However, if these are not appropriate for the data set due to an observed large correlation between corrected QT and HR using the baseline assessments, the results will also be summarized using QTcP.

ECG Summaries

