The following analyses will be performed for each applicable ECG parameters (RR, PR, QRS, QT, ventricular rate -denoted as HR in what follows-, and QTc) by treatment arm, during the on-treatment period. The denominator to calculate percentages for each category is the number of patients evaluable for the category.

- Pearson correlation between QT and HR, QTc (QTcB, QTcF and, if applicable, QTcP) and HR using individual (non-averaged) baseline assessments
- For each of the ECG parameters (HR, and QT, QTc, QRS, PR intervals), descriptive statistics at baseline, at each post-baseline time point and changes from baseline at each post-baseline time point
- Frequency (number and percentage) of patients with notable ECG values according to the following categories:
 - QT/QTc increase from baseline >30 ms, >60 ms
 - QT/QTc > 450 ms, > 480 ms, > 500 ms
 - HR ≤ 50 bpm and decrease from baseline ≥ 20 bpm
 - HR ≥ 120 bpm and increase from baseline ≥ 20 bpm
 - PR ≥ 220 ms and increase from baseline ≥ 20 ms
 - QRS ≥ 120 ms

Patients with notable ECG interval values and qualitative ECG abnormalities will be listed for each patient and time point and the corresponding notable values and abnormality findings will be included in the listings.

Unscheduled ECG measurements will not be used in computing the descriptive statistics for change from baseline at each post-baseline time point. However, they will be used in the analysis of notable ECG changes and the shift table analysis of notable QT parameters.

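### The by-arm worst-QTc tables compare 5 scheduled post-baseline ECG time points in Arm A with 2 in Arm B (6 with 3 when End of Treatment is included), so a matched-time-point comparison should be added

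*Protocol*

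**What the plan says.** Footnote 15 to the treatment-period Schedule of Activities (Protocol) sets the ECG days: "On-treatment ECGs will be performed on Days 1, 15, and 29 of Cycle 1". The number of time points on each of those days differs by arm, because the triplicates are taken "before avelumab infusion and at the end of infusion in Arm A and before sunitinib drug intake in Arm B". From Cycle 2 the schedule asks for an ECG only when clinically indicated. The end-of-treatment schedule adds one in both arms: "Triplicate ECG measurements should be performed at end of treatment, and when clinically indicated". The schedule that applies after IA3 has no 12-lead ECG row.

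The unit of analysis is the triplicate mean: "ECG measurements (an average of the triplicate measurements) will be used for the statistical analysis and all data presentations" (Protocol 9.5, Electrocardiograms). SAP 3.4.1 defines baseline: "the baseline for each ECG measurement is the average of the pre-dose replicate measurements on the baseline day".

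Three outputs rest on a worst value:
- Protocol 9.5: "Categorical analysis will be conducted for the maximum change from baseline in corrected QT and the maximum post-baseline corrected QT interval".
- Protocol 9.5 also plans shift tables from baseline to the worst on-treatment corrected QT.
- SAP 6.6.10 counts notable values by arm, among them "QT/QTc increase from baseline >30 ms, >60 ms" and absolute QT/QTc values above 450, 480 and 500 ms.

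The period covered is wide: "ECG summaries will include all ECG assessments from the on-treatment period" (SAP 6.6.10). Unscheduled ECGs enter the notable-value and shift tables. Neither document restricts these tables to time points that both arms share, or adjusts for the number of readings.

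**The concern.** The maximum of several readings tends to grow with the number of readings, even when nothing but measurement error and ordinary within-patient variation is at work. A patient read five times has more chances to pass a threshold than one read twice. The by-arm tables would then mix two things that a safety reader wants apart: a drug effect on QTc and a difference in how often QTc was looked at.

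At stake is the interpretation of the section's main comparative QT display. Part of any Arm A excess in increases above 30 ms could come from the schedule, and the planned tables cannot show how much. The HR, PR and QRS notable-value counts in SAP 6.6.10 are built in the same way. The descriptive statistics by time point are not affected.

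**Working it through.** The documents state no number of readings, no QTc SD and no exceedance rate, so there is no plan figure to reproduce. The check has two parts: a count from the schedule, and an illustration under stated assumptions.

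**Count of scheduled post-baseline time points**
- Arm A, Cycle 1: 3 days × 2 time points − 1 baseline = 5.
- Arm B, Cycle 1: 3 days × 1 time point − 1 baseline = 2.
- With an End of Treatment ECG inside the on-treatment period: 5 + 1 = 6 and 2 + 1 = 3.

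The on-treatment period ends at the earlier of 30 days after the last dose and the day before new anti-cancer drug therapy (SAP 5.2.7). So 6 vs 3 applies to patients who have an End of Treatment ECG in that window. The 5 vs 2 count applies to patients still on treatment at the cut-off, those without that ECG, and those ending treatment under the post-IA3 schedule. The gap is always three readings. Unscheduled ECGs come on top, in numbers that the plan does not fix by arm.

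**Increase above 30 ms, no drug effect**

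Assume change at reading t = e_t − e_0, where each e is the error in a triplicate mean, normal with SD s and independent between readings. Simulation of 1,000,000 patients gives P(largest change > 30 ms):

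| s (ms) | 2 readings | 5 readings | ratio 5:2 | 3 readings | 6 readings | ratio 6:3 |
|---|---|---|---|---|---|---|
| 8 | 0.76% | 1.71% | 2.25 | 1.10% | 1.99% | 1.81 |
| 10 | 3.11% | 6.44% | 2.07 | 4.35% | 7.35% | 1.69 |
| 12 | 6.85% | 13.33% | 1.95 | 9.34% | 14.97% | 1.60 |

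Hand check at s = 10: one change has SD 10√2 = 14.1 ms, and 30/14.1 = 2.12, a one-sided tail of about 1.7%. Two readings can give at most 2 × 1.7 = 3.4%, and five at most 8.5%. The simulated 3.11% and 6.44% lie below these bounds, as they should when all changes share one baseline.

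Independence is generous to the concern, because the two Arm A readings on one day are about an hour apart. With an assumed same-day error correlation:
- 6 vs 3: the ratio falls to 1.37–1.45 at correlation 0.5 and to 1.22–1.32 at 0.8.
- 5 vs 2: it falls to about 1.35–1.7 over correlations of 0.5 to 0.8.

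Across all these settings the ratio is about 1.35 to 2.25 for 5 vs 2 and 1.2 to 1.8 for 6 vs 3.

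**Increase above 60 ms.** With independent errors and 6 vs 3 readings, the rates are at most 0.11% vs 0.06% (s = 12), and under 0.01% at s = 8 to 10. With about 830/2 = 415 patients per arm, the excess is at most 0.0005 × 415 ≈ 0.2 patient.

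**Any fixed threshold.** If each reading passes with probability p, then for independent readings P(at least one of k passes) = 1 − (1 − p)^k. At p = 5%:
- 5 vs 2: 1 − 0.95^5 = 22.6% against 1 − 0.95^2 = 9.8%.
- 6 vs 3: 26.5% against 14.3%.

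With within-patient correlation 0.9 these become 9.4% vs 6.8% and 10.0% vs 8.0%. Over p = 1% to 10% and correlation 0 to 0.9, the ratio runs from 1.32 to 2.46 (5 vs 2) and from 1.21 to 1.97 (6 vs 3). Where the true p lies for 450, 480 or 500 ms cannot be read from the documents.

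**Matched time points.** With 2 vs 2 or 3 vs 3 readings and equal distributions, the ratio is 1 by construction.

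**The case against.** The best defence is that much of what is needed is already planned. SAP 6.6.10 gives descriptive statistics and change from baseline at each post-baseline time point by arm, which supply a like-for-like Day 15 and Day 29 comparison of averages. Notable values are listed by patient and time point, so end-of-infusion exceedances can be found. No formal between-arm ECG test is planned, and SAP 3.5.1 calls safety analyses generally exploratory. All of this stands, and it limits the consequence. It does not supply a matched count of patients above a threshold, which is the figure a reader would compare between arms.

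A reader might also infer four stronger things that the documents do not support:
- **That the schedule alone roughly doubles the Arm A rate.** This is near the truth only for 5 vs 2 with independent errors. For 6 vs 3 the ratio is 1.6 to 1.8 under independence, and lower with same-day correlation.
- **That a false excess must appear, including above 60 ms.** Above 60 ms the effect is negligible. More broadly, equal true distributions are an assumption. Arm B receives an active drug and is read only before intake, while Arm A is also read at end of infusion. Timing relative to dose therefore differs as well as count, and the net observed direction is unknown.
- **That Arm B's Day 29 ECG is an off-drug reading.** Four weeks of dosing end on Day 28, but the ±3 day window allows Days 26 to 32. At nominal Day 29 a Day 28 dose is about 24 hours old. Protocol 1.2.2.3 gives half-lives of about 40 hours for sunitinib and 80 hours for its active metabolite.
- **That unscheduled ECGs should leave the main tables.** Both documents place them in the outlier analysis. Triplicates are required at certain cardiac or neurologic events, so removing them could take a value above 500 ms out of the main display.

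**Conclusion.** The concern holds in a limited form. The scheduled imbalance (5 vs 2, or 6 vs 3 with End of Treatment) follows directly from the schedule. The worst-value tables take no account of it, and under equal true distributions it tilts the counts towards Arm A. The size rests on assumptions, since the documents give no QTc variability. For increases above 30 ms the ratio is plausibly between 1.2 and 2.25, depending on error SD, same-day correlation and whether an End of Treatment ECG is included. For increases above 60 ms it does not matter in practice. For the absolute thresholds and for HR, PR and QRS the mechanism is the same, but the size is not derivable. This is an interpretive weakness in a descriptive safety display. It does not touch the efficacy conclusions, and it does not predict what the data will show.

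**What to change.** In SAP 6.6.10:
1. Keep the planned all-ECG outlier and shift tables, including unscheduled ECGs, as the safety-signal display.
2. Add by-arm notable-value, maximum-change and shift tables restricted to scheduled time points common to both arms: pre-dose Day 15, Day 29 and End of Treatment. State that the between-arm comparison rests on these.
3. Show Arm A end-of-infusion ECGs in a separate table, so that any effect at that time remains visible.
4. Report the number of ECG time points per patient by arm, scheduled and unscheduled.
5. For Arm B Day 29, report time since the last sunitinib dose instead of applying a blanket label.

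Separately, the sponsor should reconcile the footnote's pre-intake ECG on Day 29 with the 4-week dosing period in Protocol 5.4.3, since nominal Day 29 has no scheduled intake to precede.

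The cost is a few extra tables and a time-point filter. No new ECGs are needed, and no planned table is lost. Matching removes the difference in count. It does not make timing relative to dose the same in the two arms, which the table notes should say.
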